#### ***Safety Analysis***

The safety end point data will be summarized for the ITT population. AEs will be categorized by System Organ Class (SOC) and Preferred Terms (PT) using the Medical Dictionary for Regulatory Activities (MedDRA) version 19.1 or higher. The incidence of AEs, as well as the intensity and relationship to study drug, will be summarized by treatment group. Safety will also be assessed by evaluating findings of physical examinations, vital signs, Local Skin Reaction Scores, clinical laboratory test results, 12-lead ECG tracings, drug exposure, concomitant medications, and withdrawals/terminations. Clinical and laboratory data will be presented by dose group. Continuous variables will be described as the mean, median, standard deviation, and minimum and maximum values of n observations. Categorical data will be described with contingency tables including frequency and percent. These findings will be

summarized and compared between treatments and within treatment groups compared to findings from baseline evaluations.

**4. LIST OF ABBREVIATIONS**

Abbreviation	Definition
β	Beta
°C	Degrees Celsius
µg	Microgram
µL	Microliter
µm	Micron
AE	Adverse event
AIDS	Acquired Immunodeficiency Syndrome
AK	Actinic keratoses
ALT	Alanine aminotransferase
AM	Morning
API	Active Pharmaceutical Ingredient
AST	Aspartate aminotransferase
AUC	Area under the plasma concentration-time curve from time zero ( $t_0$ ) to the time of the last measured sample ( $t_{last}$ )
AUC 0-τ	Area under the plasma concentration-time curve from time zero to the last measurable concentration
BID	Twice daily
BL	Baseline
BMI	Body Mass Index
CFR	Code of Federal Regulations
cm	Centimeter
C max	Peak plasma concentration
COA	Certified Ophthalmic Assistant
COT	Certified Ophthalmic Technician
CPK	Creatinine phosphokinase
CRF	Case Report Form
CRO	Contract Research Organization
D5W	5% Dextrose
dL	Deciliter
ECG	Electrocardiogram
eCRF	Electronic Case Report Form
EDC	Electronic Data Capture
EDTA	Ethylenediamine tetraacetic acid
eg	Exempli gratia, for example
EP	Electrophysiology
eRT	eResearch Technology, Inc.
FDA	Food and Drug Administration
GCP	Good Clinical Practice
GFR	estimated glomerular filtration rate
Hr(s)	Hour(s)
HIV	Human Immunodeficiency Virus
ICF	Informed Consent Form

Abbreviation	Definition
ICH	International Conference on Harmonisation
IEA	Interim Efficacy Analysis
I.e.	Id est, in other words
IID	FDA's database on Inactive Ingredients
IND	Investigational New Drug
IOP	Intraocular pressure
IRB	Institutional Review Board
IRT	Interactive Responsive Technology
ITT	Intent-to-Treat
IU	International Units
IV	Intravenous
IWRS	Interactive Web Randomization System
Kg	Kilogram
K i	Inhibition constant
L	Liter
LLOQ	Lower Level of Quantification
LSR	Local skin reaction
mcg	Microgram(s)
MedDRA	Medical Dictionary for Regulatory Activities
Mg	Milligram
Min	Minutes
mL	Milliliter
mmHg	Millimeters of mercury
[name]
MTD	Maximally Tolerated Dose
NA	Not applicable
NCE	New chemical entity
NEI	National Eye Institute
Ng	Nanogram
nM	Nanomoles
NSAID	Non-steroidal anti-inflammatory drugs
OD	Right eye
Oz / ozs	Ounce / ounces
PBS	Phosphate buffered saline
pg	Picogram
PI	Primary Investigator
pH	hydrogen ion concentration
PK	Pharmacokinetic
PM	Evening
prm	Pro re nata (as needed)
PSA	Prostate-Specific Antigen
PT	Preferred Term
QAM	Each morning

Abbreviation	Definition
QD	Once daily
QOL	Quality of Life
QPM	Each evening
QS	Quantum statis, the amount which is needed.
QTcB	QTc interval corrected using Bazett's formula
QTcF	QTc interval corrected using Fridericia's formula
SD	Standard Deviation
SAE	Serious adverse even
SAP	Statistical Analysis Plan
SOC	System Organ Class
SOP	Standard Operating Procedure
TEAE	Treatment-emergent adverse event
$t_{1/2}$	Terminal plasma half-life
$T_{max}$	Time of the peak plasma concentration
ULN	Upper limit of normal
US	United States
UVB	Ultraviolet B light
$V_{ss}$	Volume of distribution at steady state

## 5. BACKGROUND AND RATIONALE

### 5.1 Indication

VDA-1102 is a small molecule new chemical entity (NCE) under development for the treatment of patients with actinic keratosis (AK).

### 5.2 Actinic Keratosis and Current Approaches to Treatment

Actinic keratosis (AK) is one of the most common dermatologic diagnoses and affects an estimated 58 million people in the United States. Estimated treatment costs in 2004 were \$1.2 billion (Warino 2006). AK is generally present as rough patches or papules with erythema and scaling on sun-exposed skin, predominantly in older individuals with fair skin (Fitzpatrick skin types I-III). The lesions are often asymptomatic, but they may itch or be tender to the touch. Histologically, AK is characterized by keratinocyte atypia in the deeper epidermis, with defective maturation of the superficial epidermis (Cohen, 2010). The most common reason for treatment is to prevent cutaneous squamous cell carcinoma (cSCC). Although the risk of progression to invasive SCC for a specific lesion may be low, it is widely regarded that 60% to 97% of SCCs originate from AKs (Hurwitz 1995, Mittelbronn, 1998). This estimate is supported by considerable genetic analysis that demonstrates shared chromosomal abnormalities and progressive changes in gene expression between AK and SCC (Kanjilal, 1995, Ortonne, 2002, Kanellou, 2008, Padilla, 2010). Consequently, AK is often referred to as cSCC *in situ* (Heaphy, 2000, Oppel, 2004, Röwert-Huber, 2007) and is part of the continuum of transformation from normal skin to AK and cSCC (Ziegler, 1994, Stockfleth, 2013).

Since AK results from malignant processes in sun-exposed skin (mainly face, scalp, and extremities), it is often necessary to treat entire fields and not only the individual lesions. Cryosurgery and laser-based therapies are less effective for this indication. Currently the most common topical drugs and treatments for field-treatments of AK are 5-fluorouracil (5FU), imiquimod cream, ingenol mebutate gel, photodynamic therapy (PDT), and diclofenac sodium in hyaluronic acid (Chetty, 2015).

### 5.3 Unmet Medical Need

Current AK therapies are inadequate and pose significant challenges to public health. Nearly all field treatments are associated with painful severe local skin reactions ranging from necrosis to inflammation which reduce treatment compliance (Shergill 2014). Cryotherapy and surgery are used to treat a limited number of lesions. However, these may leave unsightly scars or hypopigmentation and patients often require repeat treatments.

The limited tolerability of most current treatments greatly decreases the willingness of patients to be retreated. Diclofenac sodium is the only drug available that is well tolerated.

However, it requires daily application for prolonged periods, shares the contraindications and potential side effects of the non-steroidal anti-inflammatory drug, and its long-term efficacy is still unknown. Consequently, AK patients often elect to avoid treatment and seek medical help only after their lesions have become esthetically intolerable or have advanced to invasive cSCC tumors. .

In contrast, VDA-1102 has the potential for a significantly more desirable benefit-risk ratio. The drug induces neither necrosis nor an inflammatory reaction. VDA-1102 would mitigate people's avoidance of treatment and the often required re-treatment of their chronic, recurrent skin disease.

#### 5.4 Nonclinical Summary

The two GLP toxicology studies were: 1) a 28-day repeated dose oral toxicity study in rats with a recovery phase and toxicokinetics, and 2) a 28-day topical dermal toxicity study in male and female minipigs with a recovery phase and toxicokinetics.

An MTD for the local application of VDA-1102 was not reached at the highest feasible concentration tested (20%). As discussed below in Section 5.6.2, the relative doses of VDA-1102 fed to rats and applied to the skin of minipigs were much higher than the exposures in the proposed clinical study.

Full details of the non-clinical studies performed to date are found in the accompanying Investigator's Brochure.

#### 5.5 VDA-1102 Clinical Summary

Study VDA-CP-01 (titled, "A Phase 1 Randomized, Double-Blinded, Placebo-Controlled, Dose-Escalation Study in Healthy Older-Adult Volunteers to Evaluate the Safety, Tolerability, and Pharmacokinetics of a Single Topical Dermal Application of VDA-1102 Ointment") was recently completed and preliminary blinded data are available. Healthy female volunteers without reproductive potential and male volunteers, aged 35-70, were sequentially assigned to 1 of 3 consecutive treatment cohorts (5%, 10% or 20% VDA-1102 ointment, respectively). Five subjects were randomized in a double-blind fashion in each dose cohort with 4 subjects to receive active VDA-1102 ointment and 1 subject to receive matched placebo (0% VDA-1102; vehicle control). A total of 15 subjects were randomized: 12 subjects received active VDA-1102 and 3 received placebo.

There were no deaths, serious adverse events, or early study discontinuations in this study. There were a total of 11 adverse events reported (whose treatment assignment is still unknown). All the AEs were mild, short-lived, and reversible. There were no clinically significant changes in study drug application sites, vital signs, physical examinations, clinical

laboratory results, ECGs, or Holter monitors for any individual subject at any time point regardless of treatment.

Plasma concentrations of VDA-1102 and its main metabolite, jasmonic acid were below the level of quantification of the LC/MS/MS bioanalytical assay (1 ng/mL and 50 ng/mL, respectively).

Further details of the results of this trial are provided in the VDA-1102 Investigator's brochure.

There are currently no ongoing clinical trials in which VDA-1102 is being administered.

## 5.6 Study Rationale

### 5.6.1 Rationale for Study Design and Subject Population

#### (i) Efficacy

VDA-1102 has shown relevant pharmacological effects *in vivo* in the UVB-induced SKH-1 hairless mice model of actinic keratosis and skin cancer. In this pre-clinical study, dermal application of VDA-1102 led to a significant ( $p < 0.0001$ ) reduction in the number of lesions relative to vehicle, that was comparable to the reduction noted with the comparative control compound ingenol mebutate (Picato®) 0.05%. Clinical effects were observed within a week or two of treatment initiation, although full clinical benefit was observed after 3-4 weeks.

In this clinical protocol, study drug will be applied once-daily for 28 days to the Treatment Field on the scalp or face subjects with AK. Approximately 84 male and female subjects aged 18 or older with 4-8 discrete Grade 1 and/or 2 AK lesions who sign informed consent and meet the study enrollment criteria will be randomly assigned in a double-blinded fashion to 1 of 3 parallel treatment cohorts (5% or 10% VDA-1102 ointment, or placebo) at a ratio of 1:1:1. The primary endpoint of this study is reduction in the number of AK lesions in the Treatment Field on Day 56.

#### (ii) Safety

The results from the toxicology studies and the estimated safety margins indicate that daily dermal application of 250 mg of VDA-1102 ointment for 28 days at doses as high as 20% to an area of 25 cm^2 do not pose an untoward risk for evaluation in the target patient population. Specifically, topical application once-daily for 28 days of 5% or 10% VDA-1102 ointment to 10% of the minipigs body surface area in the nonclinical toxicology program resulted in no significant systemic safety findings and only mild, reversible skin findings.

In the completed Phase 1a clinical trial (Section 5.5 above), no safety concerns were identified following a single-dose of approximately 250 mg of 5%, 10%, or 20% VDA-1102 applied once to a 25 cm^2 area on the forehead of healthy older-adult volunteers. PK analysis

demonstrated that there were no detectable concentrations of VDA-1102 or its primary metabolite, jasmonic acid.

In this study a lower dose of 200 mg of 5% or 10% VDA-1102 ointment will be applied for 28 days to an area of 25 cm^2. Safety assessments will be performed throughout the Phase 2a study. In addition, the first 15 subjects enrolled in the trial will be defined as a Nested Phase 1b Safety Sub-Cohort. Available safety data (including AEs, LSR scores, clinical laboratory results, and ECG data) from Day 1 through Day 7 from these 15 subjects will be reviewed in a blinded fashion by a safety committee consisting of 2 independent investigators (not involved in the evaluation of subjects in the study) and the Study Safety Monitor.

### **(iii) Pharmacokinetics**

In preclinical PK studies, VDA-1102 was rapidly metabolized, forming jasmonic acid as its inactive primary metabolite, regardless of the animal species or the route of administration. In all cases, the amount of JA in the blood equaled or exceeded the concentrations of VDA-1102 in the blood. In a 28-day dermal toxicity study in male and female minipigs, 5%, 10% or 20% of VDA-1102 ointment was applied once daily to 10% of the body surface area. Blood levels of VDA-1102 were essentially below the LLOQ on Day 1 and very low and highly variable on Day 28. Blood concentrations of the primary metabolite jasmonic acid on Day 1 were detected only in the 20% VDA-1102 ointment group. On Day 28, blood levels of jasmonic acid were detected at all dose levels and were higher than that on Day 1, likely related to slow transdermal absorption as it appeared that steady state levels were present on Day 28.

In the completed Phase 1a clinical trial (Section 5.5 above), there were no detectable concentrations of VDA-1102 or its primary metabolite, jasmonic acid following a single-dose of approximately 250 mg of 5%, 10%, or 20% VDA-1102 that was applied once to a 25 cm^2 area on the forehead of healthy older-adult volunteers.

In the current study, approximately 84 subjects will be dosed once each evening for 28 days with approximately 200 mg of study drug. Eighteen subjects will be enrolled into a PK Study Sub-Cohort and will undergo plasma sampling on Days 7, 14, 28, and 35 for PK assessment. Holter monitoring will be performed for 24 hours on Day 28 in all subjects enrolled in the PK Study Sub-Cohort so that relevant ECGs tracings corresponding to peak levels (if detected) of VDA-1102 and/or jasmonic acid may be extracted once the PK/exposure data are available.

#### **5.6.2 Dose and Posology Justification**

The doses to be evaluated in this clinical trial are approximately 200 mg of 0%, 5%, and 10% VDA-1102 topical ointment, spread evenly (unoccluded) over a 25 cm^2 area of skin on the face or scalp of subjects with actinic keratosis.

**Table 1** lists the mg/kg/day exposures in non-clinical toxicology studies as compared to the exposure planned in the proposed human trial. Data is presented as dose ratios rather than exposure ratios, because *in vivo*, trans-dermal absorption of VDA-1102 and its primary metabolite, jasmonic acid, appears to be minimal (minipig and human single doses) as determined with a sensitive bioanalytical assay.

The relative doses of VDA-1102 fed to rats and applied to the skin of minipigs were much higher than the highest dose (10% VDA-1102) to be applied in this study (Table 1).

**Table 1: VDA-1102 doses tested in the pivotal 28-day non-clinical studies compared to the proposed clinical doses**

Dose Group	Exposure VDA-1102 (mg/kg/day)	Exposure HED (mg/kg/day)	Exposure (mg/m  /day)	Remarks
Proposed Phase 2a Clinical Study				
Ointment 5%	0.166		6.2	
Ointment 10%	0.333		12.3	Assuming body weight of 60 kg
Exposure Levels in Completed Non-Clinical Studies:				
28-Day Oral Toxicity Study in Rats				
Low dose	100	17		
Intermediate dose	300	48		NOAEL
High dose	800	129		Mild and at least partially reversible adverse effects
28-Day Dermal Toxicity Study in Minipigs				
Ointment 5%	15	10.7	405 	NOAEL for local toxicity
Ointment 10%	30	21.4	810	Minimal local effects
Ointment 20%	60	42.9	1620	NOAEL for systemic toxicity

 Minipigs weighed <25 kg, therefore a converting factor of 27 was used.

**Tables 2** and **Table 3** compare the proposed clinical doses to the systemic HED NOEALs in mg/kg/day, and to the systemic NOAEL in mg/m^2/day, respectively, determined in the two toxicology studies performed in minipig and rat. As can be seen from these tables, the highest planned dose in early clinical studies, 200 mg of 10% VDA-1102 ointment, is approximately 135-fold below the non-clinical systemic HED NOEAL levels determined in both species, rat and minipig.

**Table 2: Comparison of the proposed clinical doses to the non-clinical HED NOAEls in mg/kg/day**

Dose Group	Exposure VDA-1102 (mg/kg/day)		
	Early Clinical Studies	NOAEL 28-Day Oral Rat (HED)	NOAEL 28-Day Dermal Minipig (HED)
Ointment 5%	0.166	48	42.9
Ointment 10%	0.333		
Ointment 20%	0.666		

**Table 3: Comparison of the proposed clinical doses to the non-clinical NOAEls in mg/m^2/day**

Dose Group	Exposure VDA-1102 (mg/m  /day)	
	Early Clinical Studies	NOAEL 28-Day Dermal Minipig
Ointment 5%	6.2	1620
Ointment 10%	12.3	

Based upon the non-clinical toxicology data and the safety findings from the Phase 1 clinical trial, VDA-1102 will be advanced to Phase 2 development. The doses in this clinical trial (200 mg of 5% or 10% VDA-1102 once daily for 28 days) are well below the nonclinical systemic HED NOEAL levels determined in both rats and minipigs. Furthermore, the daily dose proposed (~200 mg) is below the ~250 mg single dose administered in the Phase 1 clinical trial in healthy older-adult volunteers in order to more closely approximate the 200 mg dose administered in the non-clinical toxicology studies and to reduce the local and systemic exposures in humans.

## 6. STUDY OBJECTIVES

### Study Objectives:

**Primary Objective:** To compare the reduction on Day 56 in the number of the actinic keratosis (AK) lesions in the Treatment Field of subjects receiving once-daily topical 5% or 10% VDA-1102 ointment for 28 days to the reduction in the number of AK lesions in subjects receiving placebo.

### Secondary Objectives:

- To evaluate the systemic and local (skin) safety and tolerability of once-daily topical application of 5% or 10% VDA-1102 ointment or placebo for 28 days in adult subjects with AK.
- To assess the systemic exposure of VDA-1102 and jasmonic acid, its primary metabolite, at selected time points during topical application of 5% or 10% VDA-1102 ointment or placebo for 28 days in adult subjects with AK.

### Exploratory Objectives:

- To compare the proportion of subjects receiving 28 days of 5% or 10% VDA-1102 who on Day 56 had complete clearance of AK lesions to subjects receiving placebo.
- To compare the reduction on Day 84 in the number of the actinic keratosis (AK) lesions in the Treatment Field of subjects receiving once-daily topical 5% or 10% VDA-1102 ointment for 28 days to the reduction in the number of AK lesions in subjects receiving placebo.

## 7. STUDY DESCRIPTION

### 7.1 Study Design – Study Periods, Days, and Visits

Approximately 84 subjects, aged 18 or older, who sign informed consent and meet the study enrollment criteria, will be randomized to 1 of 3 parallel treatment cohorts (5% or 10% VDA-1102 ointment, or placebo) in a 1:1:1 ratio. The clinical trial will include 3 study periods (Figure 1 and Table 4).

**Screening Period** – Subjects who have given written consent to participate in the trial will undergo safety and qualifying procedures between Day -21 and Day -1 (**Screening Visit**). At this visit, the subject's Treatment Field will be identified and the subject will be trained to precisely measure and apply the study drug without actually applying ointment to their Treatment Field. Subjects unable to express the proper dose from the study drug tube and/or unable to identify their Treatment Field will be required to bring a dosing partner to the next study visit in order to proceed in the study.

Subjects who meet all the study's inclusion criteria and none of the exclusion criteria will return on Day 1 for baseline assessments to ensure they still meet the study enrollment criteria (**Day 1 Pre-Dose Visit**). During this visit, the Treatment Field selected at the Screening Visit will be requalified. If the field previously chosen fails to requalify, a new Treatment Field must be found or the subject must be excluded for failure to meet Inclusion Criterion #3 (Section 8.1). Subjects will be trained and tested twice during this visit for proper dose measurement (using the Dosing Cards 13.6.2), proper identification of the Treatment Field (using the Treatment Field Template 22.4), and precise dosing of that field using the template (stencil). Subjects (or their dosing partner) who are unable to express the proper dose from the study drug tube and/or are unable to precisely identify their Treatment Field will also be considered ineligible for the study (Inclusion Criterion #4, Section 8.1).

Subjects who continue to meet all the study enrollment criteria following the Day 1 Pre-Dose Visit will be randomized in a double-blinded fashion and proceed to the Day 1 Dosing Visit. Subjects enrolled in the PK Study Sub-Cohort will have a pre-dose blood sample drawn.

**Treatment Period** – At the **Day 1 Dosing Visit**, subjects will apply the assigned study drug (i.e., active VDA-1102 or placebo) under the supervision of site personnel. Details of the study drug application are found in Section 13.6.

From Day 1 through Day 27 subjects will apply the study each evening approximately 2 hours before bedtime. Site personnel will communicate with the subject once-weekly.

[figure not shown]
On **Day 7** and **Day 14** all subjects will return to the investigative site for safety and efficacy assessments. At each site visit, the subject's study drug will be weighed and the result will be recorded. At each visit, the subject will be re-trained in proper dose application to their Treatment Field. Subjects in the PK Study Sub-Cohort will have a blood sample taken

approximately 12 hours after their evening respective Day 6 and Day 13 evening doses. Subjects in the Nested Phase 1b Safety Sub-Cohort will undergo an additional physical examination, 12-lead ECG, and clinical laboratory assessment on Day 7.

Subjects will return to the site on **Day 28** for safety and efficacy assessments. Subjects in the PK Study Sub-Cohort will undergo blood sampling for analysis at approximately 12, 15, 18, and 21 hours after their Day 27 study drug application. Remaining study drug will be collected from all subjects at this visit.

**Observation Period** – On **Day 35** subjects will return to the site for efficacy and safety assessments. Subjects in the PK Study Sub-Cohort will undergo a single untimed blood sampling. Subjects in the PK Study Sub-Cohort will have a PK sample drawn at the time of their visit. Subjects will return to the sites on Day 56 for efficacy and safety assessments. At the End-of-Study visit on **Day 84**, final efficacy and safety assessments will be performed followed by discharge from the study. Any subject with active TEAE(s) will be followed beyond this scheduled visit until resolution.

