**Observation Period (Day 29 through 84):**

Subjects will visit their respective investigative site on **Days 35 and 56** for efficacy and safety assessments. On **Day 84** subjects will return to the sites for their final efficacy and safety assessments. Subjects with continuing AEs will be scheduled for follow-up evaluation, as appropriate.

**Nested Phase 1b Safety Sub-Cohort:** The first 15 (PK and non-PK) subjects enrolled in the trial will undergo on Day 7 the safety examinations planned for all other subjects plus physical examination, clinical laboratory and ECG assessments. Once all 15 subjects in this Nested Phase 1b Safety Sub-Cohort have completed their Day 7 Visit, safety data (including AEs, LSR scores, clinical laboratory results, and ECG data) from Day 1 through Day 7 will be reviewed in a blinded fashion by a safety committee. During this blinded interim safety review, enrolled subjects will continue dosing the study drug and study enrollment will remain open.

**PK Study Sub-Cohort:** Of the approximate 84 subjects to be enrolled in this trial, a maximum of 18 subjects at select sites will undergo blood sampling for PK analysis on Day 1 Pre-Dose as well as on Days 7, 14, 28, and 35. In addition, the PK Study Sub-Cohort will undergo 24-hour cardiac Holter monitoring on Day 28. Subjects included in this Sub-Cohort may also be included in the Nested Phase 1b Safety Sub-Cohort if they are in one of the first 15 subjects to be enrolled into the study.

**Number of Randomized Subjects (planned):** Approximately 84 (3x28) subjects will be randomized in order to complete the study with at least 75 (3x25) subjects anticipated to be available for efficacy analysis.

**Maximum Time Subjects May Remain in the Study:** Subjects may participate in this study for a maximum of approximately 117 days (21 Screening Period + 32 Treatment Period + 64 Observation Period)

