**Table 6: Table of Assessments for PK Study Sub-Cohort**

The following table indicates additional evaluations to those listed in Table 6 to be performed only in subjects enrolled in the PK Study Sub-Cohort.

Period	SCREENING PERIOD		TREATMENT PERIOD			OBSERVATION PERIOD			
	Day -21 to Day -1	Day 1		Day 7±2	Day 14±2	Day 28±4	Day 35±2	Day 56±4	Day 84±4
Study Day	Screening	Day 1 Pre-Dose	Day 1 Dosing	Day 7	Day 14	Day 28	Day 35	Day 56	Day 84
Additional Exclusion Criteria	✓								
24-hour Holter monitor attached						✓			
Toxicology screen	✓								
Blood sampling for PK 		✓		✓	✓	4 ✓	✓		

 One pre dose PK sample will be collected at the Day 1 pre-dose Visit, At the Day 7, Day 14 and Day 28 Visits, a sample will be collected when the subject arrives at the site (or approximately 12 hours after the last study drug application the previous evening). At the Day 28 Visit, three additional PK samples will be collected at 15, 18 and 21 hours (±30 mins) after the Day 27 evening dose. A final sample will be collected at the Day 35 Visit, at any time during that visit with the time noted.

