#### **10.1.4 Holter Monitoring (PK Study Sub-Cohort only)**

Subjects in the PK Study Sub-Cohort will undergo approximately 24-hours of continuous multi-lead cardiac telemetric monitoring from Day 28 (approximately 12 hours after the Day 27 dosing) through Day 29. Subjects will remove the monitors on Day 29, approximately 24 hours after they are attached, and return the Holter recorder at the Day 35 Visit.

ERT's instruction manual describes proper use and placement of these monitors. Site personnel will be trained regarding proper placement of the electrodes and recorders.

The purpose of the 24-hour cardiac Holter monitor recording is to allow ECGs to be extracted based upon the plasma PK findings.

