### ✓ **Day 1 Post-Dose through Day 6**

- Subjects will dose at home each evening, beginning with Day 1 and record the application in the Dosing Diary.

**Note: Subjects will receive 2 doses of the study drug on Day 1: once at the site after randomization and once in the evening at home.**

- Site personnel will communicate with the subjects once a week (Section 10.1.6) in order to review the Subject Instruction Packet and Dosing Diary as well as to remind each subject of their next site visit.

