- Study Drug Measurement and Application review (see Section 13.6.3)
- Study drug accountability and dosing compliance: study drug tubes will be weighed, the results recorded, and diaries reviewed and photocopied
- Study drug and study tools will be given to the subject, as needed

The following additional procedures will be performed on the Day 14 Visit only in subjects enrolled in the subjects enrolled in the PK Study Sub-Cohorts:

- ❖ PK blood sampling approximately 12 hours after the Day 13 dose
- Subject Instruction Packet will be reviewed including an appointment for the next visit will be given
- ✓ **Day 14 through Day 27**
  - Subjects will dose at home each evening approximately 2 hours before bedtime and record the application in the Dosing Diary.
  - Site personnel will communicate with the subjects once a week (Section 10.1.6) in order to review the Subject Instruction Packet and Dosing Diary as well as to remind each subject of their next site visit
- ✓ **Day 28 Visit**

On Day 28 ( $\pm 4$ ) the following procedures will be performed:

- Adverse event(s) AEs will be recorded
- Concomitant medications documented
- Vital signs: peripheral blood pressure, respiratory and heart rates, and oral temperature will be recorded
- Physical examination
- Local Skin Reaction Score in the Treatment Field
- AK Lesions in the Treatment Field: count (11.1.5) and grading (11.1.1)
- Study drug accountability and dosing compliance: study drug tubes will be weighed and the results recorded. Dosing Diaries will be collected and not returned

- 12-lead ECG tracing recorded as per the ERT manual. An original (duplicate) copy of each ECG is required. This ECG will also be transmitted to the central ECG laboratory
- Complete clinical laboratory tests: Fasting status to be recorded
- Urine pregnancy test will be performed at the investigative site in all females and the results will be recorded

The following Procedure will only be performed on the Day 28 Visit in subjects enrolled in the **PK Study Sub-Cohort**:

- ❖ PK blood sampling approximately 12 hours after the Day 27 dose. Additional blood samples will be collected at approximately 15, 18, and 21 hours post dose
- ❖ 24-hour ambulatory cardiac Holter monitor will be connected to the subject
- Trial instruction review including an appointment for the next visit will be given.

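### The Day 28 Visit may fall on Days 24 to 32, but the timed PK samples and the Holter start are tied to the Day 27 dose and fit only Day 28

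*Protocol*

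**What the plan says.** **Visit window.** Protocol Tables 4, 5 and 6 all give the Day 28 Visit a tolerance of 4 days either way, and Table 6 is the PK Sub-Cohort's own schedule. Section 12.4.2 repeats it: "On Day 28 ( $\pm 4$ ) the following procedures will be performed". SAP Tables 1, 2 and 3 carry the same window.

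**End of dosing.** Section 7.1 states: "From Day 1 through Day 27 subjects will apply the study each evening approximately 2 hours before bedtime". Section 12.4.2 adds: "Subjects will receive 2 doses of the study drug on Day 1: once at the site after randomization and once in the evening at home". Section 7.1 then gives the PK times and has leftover drug taken back: "approximately 12, 15, 18, and 21 hours after their Day 27 study drug application. Remaining study drug will be collected from all subjects at this" (the Day 28 Visit).

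**Sampling times.** Section 12.4.2 lists, for the Day 28 Visit, "PK blood sampling approximately 12 hours after the Day 27 dose", with further samples at about 15, 18 and 21 hours. The Table 6 footnote says "three additional PK samples will be collected at 15, 18 and 21 hours", with a tolerance of 30 minutes, counted from the Day 27 evening dose. Section 10.2 agrees. SAP 5.2.1.4.2.2 repeats the four times without the tolerance.

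**Holter.** Section 10.1.4 has the recording run "from Day 28 (approximately 12 hours after the Day 27 dosing) through Day 29".

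**The one flexible element.** The Table 6 footnote lets the first sample be drawn on arrival, or about 12 hours after the previous evening's application. Section 10.2 uses similar previous-evening wording for Day 28.

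**Analysis.** SAP 5.6.8.11 tabulates and plots concentrations by time point. It does not say whether time is nominal or actual, or what happens to a sample drawn outside its intended interval.

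**The concern.** Three rules meet at one visit: a nine-day window, a fixed last dosing evening, and samples timed in hours from that evening's dose. A site that uses the window as printed cannot satisfy all three.

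Systemic exposure is a secondary objective, and this is the only visit with more than one timed sample. It is also where repeat dosing could show up. Section 5.6.1 reports that in minipigs jasmonic acid was detected at all dose levels on Day 28, but on Day 1 only in the 20% group. A result below quantification several days after the last dose says little about exposure at 12 to 21 hours. The same section says the Holter is there so that ECGs matching peak levels can be extracted, and a recording started days after the last dose does not serve that purpose well.

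**Working it through.** **Inputs.** Visit day 28 ± 4 (Tables 4 to 6, Section 12.4.2). Last dose on the evening of Day 27 (Section 7.1). Samples at 12, 15, 18 and 21 h after it, the last three ± 30 min (Table 6, Section 10.2). Two doses on Day 1 (Section 12.4.2). Major deviation if dosed on fewer than 20 days (SAP 5.4.5.2.1.2). The documents give no clock time for the evening dose, so a time is assumed and varied.

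**Step 1, the window.** 28 − 4 = 24 and 28 + 4 = 32, so there are 9 permitted days. The upper end reproduces the 32-day Treatment Period in the synopsis.

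**Step 2, the day on which the samples fall.** Let the Day 27 dose be at clock time t. The 12 h sample is on Day 28 if t + 12 ≥ 24, that is, t at noon or later. The latest permitted sample, at 21.5 h, is still on Day 28 if t + 21.5 < 48, which holds for every t before midnight. For doses from 19:00 to 23:00, the 12 h sample falls at 07:00 to 11:00 and the 21 h sample at 16:00 to 20:00, all on Day 28. Any evening dose gives the same answer: 1 day of 9.

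**Step 3, the other eight days.** With a 20:00 dose and an 08:00 arrival on Day d, hours since the Day 27 dose = 12 + 24 × (d − 28). The last of the four samples comes 9 h after the first.

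| Visit day | Hours from Day 27 dose, first to last sample |
|---|---|
| 24 | −84 to −75 |
| 25 | −60 to −51 |
| 26 | −36 to −27 |
| 27 | −12 to −3 |
| 28 | 12 to 21 |
| 29 | 36 to 45 |
| 30 | 60 to 69 |
| 31 | 84 to 93 |
| 32 | 108 to 117 |

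A negative value means that the reference dose has not yet been taken. If the dose time varies from 19:00 to 23:00 with arrival kept at 08:00, the first figure becomes 37 to 33 h on Day 29 and 109 to 105 h on Day 32.

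**Step 4, early return of drug.** Full course: 1 site dose + 27 evenings = 28 applications on 27 days. If drug is collected at a visit on Day d, before that evening's dose, there are d − 1 dosing days. Day 24 gives 23 days and 1 + 23 = 24 applications, which is 4/28 = 14% fewer. Since 23 is not below 20, the SAP's dosing-days criterion does not flag it.

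**The case against.** **A site can simply book Day 28.** The Holter text names Day 28 and Day 29, and a 30-minute tolerance tells a careful coordinator which day is meant. This stands: the design can be carried out, and the window does not force an off-time sample. But Table 6 prints the wide window for exactly these subjects, so the conflict is avoidable rather than absent.

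**The first sample has an alternative.** This also stands. On Days 24 to 27 it can be drawn about 12 hours after the previous evening's dose under the Table 6 footnote, although Sections 7.1 and 12.4.2 name the Day 27 dose. The three later samples and the Holter have no such alternative.

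**The data are partly protected.** Section 10.2 records exact sampling times, SAP 5.6.8.5 uses time differences in the AUC, individual concentrations are listed, and SAP 5.6.6.9 examines days dosed. That makes the problem repairable in analysis. It does not stop the by-time-point tables from mixing different intervals.

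**The effect on means may be nil.** Single-dose human plasma levels were below quantification (Section 5.5), and about one third of the sub-cohort receives placebo. A shifted arm mean is therefore speculative, although repeat-dose levels in humans are not known from these documents.

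A reader might also infer that the synopsis count, "21 Screening Period + 32 Treatment Period + 64 Observation Period", contradicts dosing to Day 27 or is an arithmetic error. Neither follows. Section 12.3 defines the Treatment Period as ending on Day 28, not at the last dose, so 32 is 28 + 4. The 64 is Day 88 minus Day 24. The total of 117 therefore adds period maxima that one subject cannot both reach (21 + 88 = 109). It is a loose upper bound, labelled approximate, with no bearing on PK timing.

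**Conclusion.** The conflict is real and sits in the current text of both documents. Only 1 of 9 permitted visit days lets the 15, 18 and 21 hour samples and the Holter start be taken as defined. That result holds for any evening dose time. The 36 to 108 hour figures depend on the assumed 20:00 dose and 08:00 visit, and on the subject stopping on Day 27 as Section 7.1 directs. How many subjects would attend off Day 28 cannot be known from the documents.

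The reach is limited to at most 18 subjects, about 6 per arm. A reader might extend the point to Day 28 skin reaction scores, ECGs and laboratory tests, or expect late visits to lower skin reaction scores. The documents do not support this: those assessments are not defined by hours after dosing, and no recovery time course is given. The timing of the Day 56 primary endpoint is unaffected.

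**What to change.** The sponsor should reconcile four items: the last dosing day, the Day 28 Visit window for the PK Sub-Cohort, the drug-collection rule, and the dose from which PK and Holter times are counted. The places to align are the synopsis Treatment Period text, Section 7.1, Tables 5 and 6, and Sections 10.1.4, 10.2 and 12.4.2, with the matching SAP text and tables. After that, every permitted visit day should allow the samples as defined. Which rule gives way is for the sponsor to decide. The same edit should settle the 28 evenings mentioned in Section 13.6.3 and the Day 28 row in the dosing diary.

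In SAP 5.6.8, state that actual hours since the last recorded dose are used. Flag Day 28 PK and Holter values outside the intended interval rather than summarising them at the nominal time.

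The cost is small: a wording clarification and one derived variable. Sampling times (Section 10.2) and dose dates and times (Section 13.7 and the diary) are already collected, so the variable can also be derived for samples already drawn.
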